3.6.2.2 Presentation

The AEs will be presented by SOC and/or preferred term covering number and percentage of participants reporting at least 1 event and number of events where appropriate. An overview of AEs will present the number and percentage of participants with any AE, AEs with an outcome of death, Serious adverse events (SAEs), and AEs leading to discontinuation of study intervention. Separate AE tables will be provided taking into consideration the relationship to study intervention as assessed by the Investigator, intensity, seriousness, death, and events leading to discontinuation of study intervention.

AE summaries will be ordered by the international order for SOC and by decreasing frequency for preferred term within SOC.

All reported AEs will be listed along with the date of onset, date of resolution (if AE is resolved), Investigator's assessment of intensity, whether the AE is serious or not, outcome, action taken with study intervention, and possible relationship to study intervention. A by-participant listing of all AE (including AEs before first dose of study intervention) will be provided. This listing will include the following information: study period, verbatim term, MedDRA SOC and preferred term, start date/time, end date/time, time from last dose, intensity, causality, action taken, whether the AE was classified as serious, the outcome of

the AE and the concomitant or additional treatment given, if any. Any AE occurring before the first dose of study intervention and/or the AE assessments that are unresolved at the participant's last assessment in the study will be included in the data listings but will not be included in the summary tables of AEs.

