3.	To describe the relationship between changes from baseline (week 0) in airway dynamics and conventional lung function measurements at week 13, after accounting for baseline measurements of conventional lung function.	Correlation between the change from week 0 in imaging endpoints (primary and secondary FRI endpoints ^b) at week 13 and the change from week 0 in pre-BD FEV ₁ at week 13 (\pm 5 days), overall and within subgroups conditional on the baseline value of pre-BD FEV ₁ . Correlation between the change from week 0 in imaging endpoints (primary and secondary FRI endpoints ^b) at week 13 and the change from week 0 in pre-BD FVC at week 13 (\pm 5 days), overall and within subgroups conditional on the baseline value of pre-BD FVC at week 13 (\pm 5 days), overall and within subgroups conditional on the baseline value of pre-BD FVC.	

	Scatter plots of changes from week 0 in primary and secondary FRI endpoints ^b at week 13 vs. changes from week 0 in conventional lung function measures (pre-BD FEV ₁ and pre-BD FVC) at week 13. Estimated change over time (week 13 vs. week 0) in primary and secondary FRI endpoints ^b , with and without adjustment for conventional lung function measures (pre-BD FEV ₁ and pre-BD FVC).	
Safety		
To monitor the safety and tolerability of benralizumab.	 Safety and tolerability will be evaluated in terms of AEs, Vital signs, and Clinical laboratory. Assessments related to AEs include: Occurrence/Frequency Relationship to IP or study procedure as assessed by investigator Intensity Seriousness Death AEs leading to discontinuation of IP Other significant AEs Time to onset Vital signs parameters include systolic and diastolic blood pressure and heart rate. 	
 a. FRI endpoints are untrimmed unless otherwise specified. b. The primary FRI endpoint is total mucus volume at TLC; secondary FRI endpoints for evaluation under secondary objectives include: total mucus plugs score at TLC, total air trapping at FRC; trimmed distal iVaww at TLC; trimmed distal siVaw at TLC and FRC; total iVlung at TLC and FRC; and total mucus plugs score at TLC. 		

AE = adverse event; FEV₁ = Forced expiratory volume in 1 second; FRC = Functional residual capacity; FRI = Functional Respiratory Imaging; FVC = Forced vital capacity; IP = investigational product; iVaww = Airway wall volume; iVlung = Lung volume; siVaw = Specific airway volume; TLC = Total Lung Capacity.

For CCI

objectives and endpoints, see Section 3 of the protocol.

Overall Design

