8.4.1 Time Period and Frequency for Collecting AE and SAE Information

Adverse events will be collected from after the participant received the first dose of the study intervention, throughout the treatment period and including the follow-up period (Visit 5, last contact), or up until follow-up for early discontinuation.

SAEs will be recorded from the time of signing of the informed consent form.

If the investigator becomes aware of a serious adverse event with a suspected causal relationship to the investigational medicinal product that occurs after the end of the clinical study in a participant treated by him or her, the investigator shall, without undue delay, report the serious adverse event to the sponsor.

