8.4.2 Follow-up of AEs and SAEs

Any AEs that are unresolved at the participant's last AE assessment or other assessment/visit as appropriate in the study are followed up by the investigator for as long as medically indicated, but without further recording in the eCRF. AstraZeneca retains the right to request additional information for any participant with ongoing AE(s)/SAE(s) at the end of the study, if judged necessary.

Adverse event variables

'The following variables will be collected for each AE;

- AE (verbatim)
- The date when the AE started and stopped
- Intensity of the AE
- Whether the AE is serious or not
- Investigator causality rating against the Investigational Product (yes or no)
- Action taken with regard to Investigational Product
- AE caused participant's withdrawal from study (yes or no)
- Treatment for AE
- Outcome
- Causality assessment in relation to study procedure (yes or no)

In addition, the following variables will be collected for SAEs:

- Date AE met criteria for SAE
- Date investigator became aware of SAE
- AE is serious due to
- Date of hospitalization
- Date of discharge
- Probable cause of death
- Date of death
- Autopsy performed
- Causality assessment in relation to study procedure(s)
- Causality assessment to other medication
- AE description

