8.4.3 Causality Collection

The investigator should assess causal relationship between IMP, Investigational Medical devices and/or study procedure and each AE and/or Incident, and answer 'yes' or 'no' to the question 'Do you consider that there is a reasonable possibility that the event may have been caused by the investigational product?'

For SAEs and Serious Incidents, causal relationship should also be assessed for other medication and study procedures and/or medical devices. Note that for SAEs that could be associated with any study procedure the causal relationship is implied as 'yes'.

A guide to the interpretation of the causality question is found in Appendix C to the Clinical Study Protocol. For medical devices, a guide to the interpretation of the causality question can be found in Appendix E.

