9.4.3 Safety

Safety analyses will be performed using the safety analysis set. Adverse events will be coded using the most recent version of the Medical Dictionary for Regulatory Activities that will have been released for execution by the Sponsor/designee.

Safety data will be presented using descriptive statistics unless otherwise specified.

The AEs will be presented by system organ class and/or preferred term covering number and percentage of patients reporting at least 1 event and number of events where appropriate. An overview of AEs will present the number and percentage of patients with any AE, AEs with outcome of death, SAEs, and AEs leading to discontinuation of IP. Separate AE tables will be

provided taken into consideration relationship as assessed by the Investigator, intensity, seriousness, death, and events leading to discontinuation of IP. An additional table will present number and percentage of patients with the most common AEs.

Vital signs

Vital sign parameters will be presented for each treatment group. Summary statistics for continuous variables cover n, mean, SD, Min, Q1, median, Q3, and Max.

Details of vital sign analyses will be provided in the SAP.

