3.6 Safety Analyses

All safety variables will be summarized using the safety analysis set and data presented according to actual treatment received.

Safety data will be presented using descriptive statistics unless otherwise specified.

All safety measurements will use all available data for analyses, including data from unscheduled visits and repeated measurements.

The domain safety covers exposure, Adverse events (AEs), clinical laboratory, vital signs, and ECG results.

Tables and listings are provided for the safety set.

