3.6.2 Adverse Events

3.6.2.1 Definitions and Derivations

AEs are collected from the time of first dose of IP, throughout the treatment period and until Week 15 safety follow-up period is completed. AE causality is as determined by the reporting investigator. AEs with date of onset on or after the earliest first dose of any of the components of the combination should be considered to be treatment emergent.

AEs will be coded using the most recent version of MedDRA that will have been released for execution by the Sponsor/designee.

Multiple occurrences of an AE in the same participant will only be counted once overall considering start date as the first day of first occurrence and stop date the last day of the last occurrence.

In the case that, during the study, a participant has more than one episode of the same preferred term with different levels of intensity, then the maximum intensity level will be used. The following ordering will be used to define maximum intensity level: Mild < Moderate < Severe.

For each participant and each AE, the worst severity recorded will be attributed and used in the by-severity summaries. Similarly, the worst causality (most related to study intervention) will be attributed and used in the by-causality summaries. If severity or causality is missing, a conservative approach for AE assessment (taking into account the worst case) will be followed.

Any AEs with incomplete start and end dates/times will be treated as follows:

- AEs with unknown start times, but with start date known, will be imputed with a time of 00:00, unless the start date corresponds to any given dosing date. In this case the start time will be imputed with the time of dosing. If this results in a start date/time after end date/time of the AE, then the time will also be imputed with 00:00.
- AEs with completely unknown start dates will be imputed with the date and time of dosing unless the end date is known and prior to dosing; in that case the start date will be imputed as the date of screening and a time of 00:00.
- AEs with partially known start dates/times will be treated as follows:

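### Adverse event relationship to study procedure is a protocol safety outcome collected for every event, but the SAP summarises relationship to study intervention only, and serious events in undosed participants have no assured output

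*SAP*

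**What the plan says.** **Protocol.** The safety outcomes in the Synopsis, repeated in Table 2 of Section 3, give eight attributes under which adverse events are assessed. One is "Relationship to IP or study procedure as assessed by investigator". Section 8.4.2 puts two causality items among the variables taken for each event: a yes/no rating against the product, and "Causality assessment in relation to study procedure (yes or no"). Section 8.4.3 sets the matching duty: "The investigator should assess causal relationship between IMP, Investigational Medical devices and/or study procedure and each AE and/or Incident". Section 9.4.3 says that separate adverse event tables will be "provided taken into consideration relationship as assessed by the Investigator", with no limit to the product. On timing, Section 8.4.1 starts non-serious events at the first dose, but "SAEs will be recorded from the time of signing of the informed consent form". Section 5.4 keeps serious events in the minimum data set for screen failures.

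**SAP.** Section 3.6.2.2 states: "Separate AE tables will be provided taking into consideration the relationship to study intervention as assessed by the Investigator". Section 3.6.2.1 adds that "the worst causality (most related to study intervention) will be attributed and used in the by-causality summaries". Section 3.6.2.2 describes two listings. The first carries only the possible relationship to study intervention. The second is by participant, covers all events including those before the first dose, and has one field called causality. Events before the first dose, and those unresolved at the last assessment, go to listings and stay out of the summary tables. On population, Section 3.6 says: "Tables and listings are provided for the safety set".

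**The concern.** A stated safety outcome that is already being collected should have a planned result. Here the product half has one and the procedure half does not.

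The procedure half matters in this trial. Benralizumab is given under its approved regimen, whereas the CT scans are added by the study, and Protocol section 2.3.1 ties the risks of the study design to CT. Section 8.1.1 asks sites to record abnormalities found on the scans as adverse events. Maintenance and rescue therapy is also withheld before Visits 0, 1 and 4. If the SAP is followed as written, the report can say how many events occurred and how many were attributed to benralizumab. It cannot say, from any planned summary, how many were attributed to the procedures.

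The second strand is timing. Protocol section 6.2 places dosing after all other Visit 1 assessments, so the Visit 0 and Visit 1 procedures come before the first dose. In that window only serious events are collected, and a participant who has one may never be dosed.

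**Working it through.** No arithmetic beyond counting applies. The check sets the texts side by side.

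1. *Is procedure relationship a planned outcome?* Yes. It is in the Synopsis and in Table 2, as one half of one of eight listed attributes.
2. *Is it collected?* Yes. Protocol section 8.4.2 has two causality fields per event, one for product and one for procedure.
3. *Does the protocol limit the relationship tables to the product?* No. Section 9.4.3 refers to relationship without qualification.
4. *Does the SAP plan a summary of it?* No. The relationship table (3.6.2.2) and the worst-causality rule (3.6.2.1) both refer to study intervention. Of the two collected fields, one is summarised.
5. *Does a listing show it?* Not assuredly. The first listing names study intervention only. The second has one undefined causality field, which could hold the product rating, the procedure rating or both.
6. *Does the Addendum fill the gap?* No. Its changes to safety outputs concern vital signs (2.12) and the ECG, medical history and pregnancy listings (2.13).
7. *Where do procedure-related events go?* With onset on or after the first dose and resolved, they enter the overall, organ-class, seriousness, intensity and discontinuation tables whatever their cause. Before the first dose or unresolved, they are listed only.
8. *How much procedure exposure comes before dosing?* Two of each participant's four scans (those at Visit 1), and two of the three visits that require withheld medication (Visits 0 and 1).
9. *What covers a serious event in an undosed participant?* Both documents define the safety set by at least one dose (Protocol Table 8; SAP Table 1), and Protocol section 9.4.3 runs the safety analyses on it. SAP section 3.6 applies it to listings as well as tables. SAP section 3.6.2.2 says that all reported events are listed, including those before dosing. On the first text the event is left out; on the second it may be included. Nothing in the SAP settles which governs.

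**The case against.** The strongest reply is that nothing is hidden. A reader might infer that harms of the procedures go unreported, and the documents do not support that. Resolved events after the first dose are counted in the overall tables whatever their cause, and the rest are listed. What is missing is attribution to the procedure.

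A reader might also infer that the SAP departs from the protocol by limiting safety output to dosed participants. It does not: the protocol sets the same population. Nor can it be said that serious events in undosed participants reach no output at all, because that takes one side of an unreconciled conflict within the SAP as settled. These events are in any case recorded and reported to the sponsor under Protocol section 8.4.7.

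Three further limits are fair. Non-serious events before the first dose are outside the protocol's collection period, so no SAP table can recover them. Exacerbations are adverse events only if they are serious or lead to discontinuation of the product (Protocol sections 8.3.1 and 8.4.6), so a procedure table would show only part of any harm from withheld medication. And the outcome is one half of one attribute in a descriptive, single-arm study with an estimated 38 enrolled.

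These points limit the size of the concern but leave its core. The outcome is named, the answer is collected for each event, and no summary uses it.

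**Conclusion.** The point holds in this form. AE relationship to study procedure is a protocol safety outcome with a yes/no answer for each event, and the SAP plans no summary of it and no listing column that assuredly shows it. Procedure-related events would be counted or listed without being reliably identifiable as such. Serious events in enrolled but undosed participants have no assured output, because the safety set requires a dose in both documents and SAP sections 3.6 and 3.6.2.2 conflict on the scope of listings.

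The size is one of two collected causality fields without a planned summary, plus an unsettled population for one class of serious event. The number of events affected cannot be known from the documents. Efficacy results and the treatment-emergent tables are not touched. The conclusion assumes that the outputs follow the SAP and Addendum as written. If the undefined causality field was meant to show both ratings, the listing gap closes but the summary gap remains. The change should be made, because a stated outcome would otherwise have no summary.

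**What to change.** In SAP section 3.6.2, by a further addendum:

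- Add a row to the adverse event overview, and one table by system organ class and preferred term in the safety set, for adverse events and serious adverse events assessed as related to study procedure. State in the table note how events before the first dose and unresolved events are handled.
- Derive worst causality separately for study intervention and for study procedure.
- Show the two causality fields in separate listing columns.
- Reconcile SAP section 3.6 with section 3.6.2.2 by listing all serious adverse events from informed consent in the enrolled set, flagged as before or after the first dose and as dosed or not dosed.

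The existing treatment-emergent tables stay as they are. The cost is wording, one overview row, one table, one listing and one extra listing column, with no new data and no change to participant management. There is precedent for both parts. Addendum section 2.12 restored vital-sign tables because listing alone contradicted the protocol, and the SAP already lists asthma history and medications for enrolled participants (3.1.6.2 and 3.1.8.2).

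### The SAP keeps adverse events still unresolved at the last assessment out of the AE summary tables, so reported incidence is biased downward

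*SAP*

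**What the plan says.** SAP Section 3.6.2.2 ends with a rule covering two groups of AE, joined by and/or. One is any AE before the first dose. The other is described as follows: "AE assessments that are unresolved at the participant's last assessment in the study will be included in the data listings". The sentence then completes the rule for both groups: "but will not be included in the summary tables of AEs".

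Other parts of the plan bear on the same tables:

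- Earlier in the same SAP section: "An overview of AEs will present the number and percentage of participants with any AE". Deaths, serious AEs (SAEs) and AEs leading to discontinuation are in that overview too.
- Protocol Section 9.4.3: "An overview of AEs will present the number and percentage of patients with any AE", with the same further categories and no condition on resolution.
- SAP Section 3.6: "All safety measurements will use all available data for analyses, including data from unscheduled visits and repeated measurements".
- SAP Section 3.6.2.1: "AEs are collected from the time of first dose of IP, throughout the treatment period and until Week 15 safety follow-up period is completed". The same section defines treatment emergence by date of onset alone.
- Protocol Section 8.4.2: AEs unresolved at the last assessment "are followed up by the investigator for as long as medically indicated, but without further recording in the eCRF".

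**The concern.** Excluding events before first dose is ordinary practice, because they are not treatment-emergent. Excluding events because they have not resolved is different: it conditions the numerator of an incidence on outcome and duration. A participant who develops a lasting AE under treatment would not be counted for that event, while one whose AE cleared up would be.

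The study's own schedule makes the loss selective:

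- The Week 15 contact is only for participants who completed three doses (Protocol Table 1). For those who stop early, AE collection ends at the early-discontinuation follow-up (Protocol Section 8.4.1). An AE that caused discontinuation may well be ongoing then, so the table of AEs leading to discontinuation is directly exposed.
- New or recurrent malignancy is a listed reason for discontinuation (Protocol Section 7.1) and is unlikely to have resolved by that visit.
- Abnormalities seen on CT are to be recorded as AEs (Protocol Section 8.1.1). The post-treatment CT is at Week 13, about two weeks before last contact, so a new finding may still be present.

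Safety and tolerability is a stated objective, with AE occurrence and frequency first among its AE measures. The summary tables are its main output.

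**Working it through.** **1. Reading the rule.** The conjunction is and/or, so non-resolution is a ground for exclusion by itself. An AE that began after first dose and is still ongoing at the last assessment meets it. No exception is made for SAEs, related AEs or AEs leading to discontinuation.

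**2. Comparison with the rest of the plan.**

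| Place | What determines inclusion in AE summaries |
|---|---|
| SAP 3.6.2.2, last sentence | Onset on or after first dose **and** resolved by last assessment |
| SAP 3.6.2.2, overview | Any AE |
| SAP 3.6.2.1 | Treatment-emergent by onset only |
| SAP 3.6 | All available data |
| Protocol 9.4.3 | Any AE, no resolution condition |

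Protocol 8.4.2 limits data recording after the last assessment. It does not remove an event already recorded. The SAP Addendum changes the presentation of vital signs (2.12) and some listings (2.13), but not the AE tables.

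**3. Share of events affected.** The documents give no AE durations and no figure to reproduce, so this step rests on assumptions: onset uniform over T = 15 weeks from first dose to last contact, and exponential duration with mean m weeks. The probability that an AE is ongoing at T is

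(1/T) ∫₀ᵀ exp(−(T − t)/m) dt = (m/T) × (1 − exp(−T/m))

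- m = 2: (2/15) × (1 − exp(−7.5)) = 0.133
- m = 4: (4/15) × (1 − exp(−3.75)) = 0.260
- m = 8: (8/15) × (1 − exp(−1.875)) = 0.452

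A condition that does not resolve is missed every time. For participants who leave early, T is shorter and the share is larger.

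**4. Effect on an incidence.** Reported incidence = true incidence × (1 − u), where u is the share of affected participants whose event is unresolved. The size of the safety set is not stated. Take 38 (planned enrolment) for illustration and assume 10 participants have a given AE, a true incidence of 10/38 = 26.3%.

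| Unresolved among the 10 | Reported incidence |
|---|---|
| 1 | 9/38 = 23.7% |
| 3 | 7/38 = 18.4% |
| 5 | 5/38 = 13.2% |
| 10 | 0% |

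One omitted participant is worth 1/38 = 2.6 points, or 1/34 = 2.9 points if the denominator is the 34 planned as evaluable.

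**5. The any-AE row.** A participant leaves this row only if all of their AEs are unresolved. If AEs were independent with share 0.260, that is 26.0% of those with one AE, 0.260² = 6.8% with two, and 0.260³ = 1.8% with three. Counts by preferred term, system organ class, intensity, causality and seriousness are therefore more exposed than the headline row.

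**The case against.** The best defence is that the clause is a drafting slip. It speaks of unresolved AE assessments, not unresolved AEs, and may be a garbled carry-over of the follow-up rule in Protocol Section 8.4.2. Everything else in the SAP points toward counting all treatment-emergent events. That may be how the sentence arose, but a programmer working from the SAP would apply the filter as written, and nothing in the SAP or Addendum says otherwise.

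Four further points limit the claim:

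- The excluded events stay in the by-participant listings, with onset, seriousness, outcome and relationship. In a study this small a reader could recount them. They are lost from reported incidence, not from the report.
- Protocol Section 8.4.2 lets the sponsor ask for more information on ongoing events, and Section 8.4.7 requires SAE updates. Later outcome information can therefore reach the sponsor. The SAP rule, however, fixes status at the last assessment, so a later resolution would not return the event to the tables.
- The percentages are shares of events under assumed durations, and the any-AE row loses less. Fatal AEs have a final outcome, so the death table is not obviously affected.
- Safety is descriptive, with no comparator, and expedited SAE reporting does not depend on these tables. The primary endpoint is untouched.

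These points bound the consequences. They do not remove the contradiction or the direction of the bias.

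**Conclusion.** The concern holds. As written, the last sentence of SAP Section 3.6.2.2 removes unresolved treatment-emergent AEs from the summary tables, contrary to Protocol Section 9.4.3 and to SAP Sections 3.6 and 3.6.2.1. That the bias is downward needs no assumption, since dropping events can only lower counts. Its size is not knowable from the documents: the 13% to 45% range depends on uniform onset over 15 weeks and mean durations of 2 to 8 weeks, and the per-participant shift on a denominator of 34 to 38. It should be corrected before the AE tables are produced, because the main output for a stated objective would otherwise be understated by rule.

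**What to change.** In the last sentence of SAP Section 3.6.2.2, delete the clause on AE assessments unresolved at the last assessment and keep only the exclusion of AEs before first dose. Add that every AE with onset on or after first dose is included in the summary tables whatever its outcome, with the outcome of unresolved events given as not recovered or ongoing. The existing listing already carries outcome, so a separate outcome table is optional.

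The cost is one sentence in the SAP or its Addendum and one filter in the AE table programs. No new data are needed, because onset and outcome are already collected.
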